Three affect classifiers are trained, one with the original 4-classes, one for valence (showing the pleasantness of emotion) and one for arousal (reflecting the activity/vitality of the speaker). The arousal and valence labels are obtained by clustering the original 4-classes into corresponding binary labels (e.g. Happy to positive valence and high arousal, Anger to negative valence and high arousal). The predictions of these affect classifiers are then used as mid-level features to classify bipolar disorder.

Video Processing and Visual Features

The faces are detected, cropped and registered using the method proposed by Xiong and De la Torre (2013) with additional procrustes analysis for frontalization as in (Kaya et al., 2015). Along with the faces, we record both the original and the aligned landmark points for subsequent geometric feature extraction. Also, we extract appearance descriptors from registered faces, using a pre-trained Deep Convolutional Neural Network (DCNN) fine-tuned on a face based emotion corpus (Kaya et al, 2017). From DCNN, we extracted 4096 dimensional features from a convolutional layer and 7 dimensional features (outputs for 7 basic emotions) from the last layer.

Neurocognitive Evaluation

Cambridge Neurophysiological Assessment Battery (CANTAB) are administered to both groups) to assess neurocognitive functions. For patients both in the manic phase(in the first week of hospitalization) and in the remission (at 3rd month after beginning of mania treatment), tests are applied. Applied four different tests and their outcome measures are explained below :

Cambridge Gambling Test: Deliberation time, quality of decision making , risk taking, aversion delay

Emotion Recognition Test: Total rate of happiness, sadness, anger,disgust, fear, surprise

Stop Signal Test: Rate of succesful stops, reaction time, delay of stop signal, reaction time for stop signal, total of true stops

Rapid Visual Processing: Outcome measures cover latency (speed of response), probability of false alarms and sensitivity.

Study groups' sociodemographic and clinical features are defined. Bipolar manic phase patients' first YMRS ratings are correlated with first week neurocognitive functions of the same group. The comparison of bipolar mania neurocognitive functions with both bipolar remission and healthy controls are evalauted. The voice analysis results correlation with neurocognitive functions in bipolar mania is examined.

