Correlation of Audiovisual Features
With Clinical Variables and
Neurocognitive Functions in Bipolar
Disorder, Mania

01.08.2017

Statistical Analysis

Speech and Video Analysis

Classification Methods

Feature vectors extracted from audio and video are modelled using Partial Least Squares (PLS) regression and Extreme Learning Machines based classifiers(Kaya et al., 2015; 2017).

Neurocognitive Evaluation

Statistical evaluation is done by using SPSS(Statistical Package for Social Sciences) for Windows 18.0 program. Categoric variables are compared with Chi-square test, qualitative variables are compared with dependent and independent sampling t-test and Mann- Whitney U test. Correlation analysis are done with Pearson and Spearman test. Statistical significance is *= $p<0.05$, **= $p<0.01$, all of tests are two-sided.

Emotion predictions for Pearson correlation analysis and regression of YMRS drop

Regression Model

YMRS score temporal change is calculated as, $t1=0$ th day, $t2=3$ rd day, $t3=7$ th day, $t4=14$ th day, $t5= 28$ th day, $t6=90$ th day and $X1=t2/t1$, $X2=t3/t1$, $X3=t4/t1$, $X4=t5/t1$ and $X5=t6/t1$. These proportions are regressed as stepwise linearly to valence, arousal and singular affect scores of first audio recording values.

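### The mania-to-remission CANTAB comparison estimates recovery plus any practice gain, because remission is always the second session and no control retest is stated

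*Protocol*

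**What the plan says.** The Neurocognitive Evaluation section of the protocol says of the battery: "Cambridge Neurophysiological Assessment Battery (CANTAB) are administered to both groups) to assess neurocognitive functions". It then gives a testing schedule for patients only: "For patients both in the manic phase(in the first week of hospitalization) and in the remission (at 3rd month after beginning of mania treatment". It gives no number or timing of sessions for controls.

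The closing paragraph of that section lists the planned analyses. The group and phase comparison is: "The comparison of bipolar mania neurocognitive functions with both bipolar remission and healthy controls are evalauted". This yields two contrasts, mania versus remission (within patient) and mania versus healthy controls (between groups). The two planned correlations use manic-phase scores: "Bipolar manic phase patients' first YMRS ratings are correlated with first week neurocognitive functions of the same group", and "The voice analysis results correlation with neurocognitive functions in bipolar mania is examined".

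The Neurocognitive Evaluation section of the SAP supplies the tests. For these comparisons they are the "dependent and independent sampling t-test" and the Mann-Whitney U test, two-sided, with significance at 0.05. Neither document mentions alternate test forms, a familiarisation session, a practice adjustment, a group-by-time contrast, or remission versus controls.

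**The concern.** Phase and session order coincide completely in the patients: mania is session one and remission is session two. Any gain from having met the tasks before has the same sign in every remission-minus-mania difference as a real improvement would, wherever practice improves the score. Controls enter only the mania contrast, so matching them on age, gender and education does not help here.

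What is at stake is the interpretation of one result. A significant mean change between phases could be reported as cognitive improvement with remission when part or all of it comes from testing twice. The planned analyses contain nothing that would let a reader tell the two apart.

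**Working it through.** **Inputs from the documents.** Patients: 35 + 16 = 51. Controls: 24 + 16 = 40 (both from the opening part of the protocol). Two-sided alpha is 0.05 (SAP). The documents give no power, effect-size or sample-size figure for CANTAB, so there is none to reproduce.

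**Assumptions.** The practice gain g (in SD of a single score), the test-retest correlation r and the number of complete pairs n are not in the documents. They are varied below. True recovery is set to zero.

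**Step 1: what each contrast estimates.**
- Remission minus mania, same patients: recovery + practice (+ any other effect of time). This is one equation with two unknowns.
- Mania versus controls: the manic-phase deficit, free of practice if controls are also at their first session.

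The second contrast holds no information on practice, so it cannot resolve the first.

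**Step 2: chance of significance with zero recovery.** The standardised paired difference is dz = g / √(2(1 − r)), and the noncentrality is dz × √n. With r = 0.5 the divisor is √1 = 1, so dz = g. With n = 51, √51 = 7.141, so g = 0.2 gives a noncentrality of 0.2 × 7.141 = 1.428 against a critical t (50 df) of 2.009. The noncentral t then gives 28.8%.

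| Assumed gain g | r = 0.5, n = 51 | r = 0.7, n = 51 | r = 0.5, n = 30 |
|---|---|---|---|
| 0.1 SD | 10.8% | 14.8% | 8.3% |
| 0.2 SD | 28.8% | 44.0% | 18.5% |
| 0.3 SD | 55.6% | 77.4% | 35.5% |

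With r = 0.3 and n = 51 the figures are 9%, 22% and 43%. At g = 0 each cell is 5%.

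**Step 3: patient change versus control change, if controls were retested.** In a simulation with equal practice in both groups and zero recovery (51 versus 40, gains of 0.2 to 0.4 SD of change), the two-sample test on change rejected in about 4.9% of runs. The recovery detectable with 80% power is (1.960 + 0.842) × √(1/51 + 1/40) = 0.59 SD of change. For the paired test it is 2.802 / √51 = 0.39, but that test detects recovery and practice together.

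**Step 4: regression of CANTAB change on YMRS change.** A practice gain equal in all patients goes into the intercept. Simulated at n = 51 with no true slope and uniform gains of 0, 0.2 and 0.3 SD of change, the slope test rejected in about 5% of runs. If practice itself varies with YMRS change, by an assumed 0.1, 0.2 or 0.3 SD of change per SD of YMRS change, it rejected in about 11%, 28% and 54%. Power: tanh(2.802 / √48) = 0.38, so 51 patients give 80% power only for a correlation of about 0.38. With 30 patients it is tanh(2.802 / √27) = 0.49.

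**Step 5: remission versus controls.** With 51 versus 40 the power at d = 0.60 is 80.2%. If controls are tested once, this compares a second session with a first.

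**The case against.** The strongest reply is that the plan promises only a comparison of scores between phases. A paired t-test asks whether the mean scores differ. If practice shifts the mean, they do differ, and rejecting is correct. On that view the percentages above are power against a real difference. This stands: a reader might infer that the planned test fails to hold its 5% error rate, but that is so only if the change is then read as recovery, a claim neither document makes. The point is one of interpretation.

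Second, the size rests entirely on assumptions, and 51 pairs presumes that nobody is lost before a visit after discharge. This also stands, which is why 30 pairs are shown as well.

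Third, a reader might infer that controls were tested only once. The documents are silent, and silence does not establish that.

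Fourth, the absence of remission versus controls might be called an error. The planned neurocognitive analyses centre on mania, and persistence of a deficit in remission is not a stated question, so the contrast is a useful addition, not a missing requirement. It would not remove practice either. For measures such as risk taking, deliberation time or stop-signal delay, the documents state no better direction, so practice cannot be assumed to bring every score closer to controls.

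Fifth, the YMRS regression may fail in the same way as the paired test. Patients first meet the tasks during acute mania, and severity could affect how much they learn. Step 4 shows that the distortion can then be as large as the original one.

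None of this removes the confounding of phase with session order. It limits what the supportive analyses can show and how strongly the point may be put.

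**Conclusion.** The concern holds in a limited form, as a low-cost improvement to the SAP. The dependent test of mania versus remission estimates recovery plus any practice gain, and nothing planned separates the two. Other effects of time, such as changes in treatment or selective return at month 3, may be mixed in as well.

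The amount of bias is unknown and may differ by outcome. For assumed gains of 0.1 to 0.3 SD with r = 0.5, the chance of a significant change without recovery runs from 11% to 56% with 51 pairs and from 8% to 36% with 30. Higher test-retest correlation raises these figures and lower correlation reduces them. Mania versus controls is unaffected if controls are at their first session. No analysis of the existing data fully separates practice from recovery unless controls were retested.

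**What to change.** In the neurocognitive section of the SAP:

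1. State how many times, and when, controls took CANTAB. If they were retested, compare patient change with control change. The price is precision: a detectable recovery of about 0.59 SD of change, with 51 and 40 complete.
2. If they were not retested, report the mean mania-remission change as recovery plus possible practice, with the number of complete pairs. Rest any claim of a manic-phase deficit on mania versus controls, provided controls are at their first session.
3. Add two supportive analyses on data already planned:
   - Regress CANTAB change on YMRS change, naming in advance which first-week YMRS rating is used. State that this addresses association and not mean change, is protected only against practice unrelated to YMRS change, and has 80% power only for a correlation of about 0.38 at n = 51.
   - Compare remission with controls. A remaining deficit is conservative evidence of persistence only for outcomes on which practice moves scores toward controls. A finding of no difference is uninterpretable.

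The cost is SAP wording, a few more tests and a more cautious conclusion on mean recovery. No new visit or procedure is needed.

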Correlation of Audiovisual Features
With Clinical Variables and
Neurocognitive Functions in Bipolar
Disorder, Mania

01.08.2017

Statistical Analysis

Speech and Video Analysis

Classification Methods

Feature vectors extracted from audio and video are modelled using Partial Least Squares (PLS) regression and Extreme Learning Machines based classifiers(Kaya et al., 2015; 2017).

Neurocognitive Evaluation

Statistical evaluation is done by using SPSS(Statistical Package for Social Sciences) for Windows 18.0 program. Categoric variables are compared with Chi-square test, qualitative variables are compared with dependent and independent sampling t-test and Mann- Whitney U test. Correlation analysis are done with Pearson and Spearman test. Statistical significance is *= $p<0.05$, **= $p<0.01$, all of tests are two-sided.

Emotion predictions for Pearson correlation analysis and regression of YMRS drop

Regression Model

YMRS score temporal change is calculated as, $t1=0$ th day, $t2=3$ rd day, $t3=7$ th day, $t4=14$ th day, $t5= 28$ th day, $t6=90$ th day and $X1=t2/t1$, $X2=t3/t1$, $X3=t4/t1$, $X4=t5/t1$ and $X5=t6/t1$. These proportions are regressed as stepwise linearly to valence, arousal and singular affect scores of first audio recording values.

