Correlation of Audiovisual Features
With Clinical Variables and
Neurocognitive Functions in Bipolar
Disorder, Mania

01.08.2017

Study Protocol

In order to gather sociodemographic and clinical information, all patients were assessed with semi-structured interviews based on the SKIP-TURK. This form includes: identity, sociodemographic personal and family information, age at disease onset, severity, clinical presentation and used treatments.

Thirty-five male and sixteen female patients who were diagnosed as BD type I, manic episode according to DSM-5 in the mental health service of Erenkoy Mental State Hospital and 24 male and 16 female healthy controls matched for age, gender, educational status were included. During hospitalization in every follow up day (0th- 3rd- 7th- 14th- 28th day) and after discharge on the 3rd month, presence of depressive and manic features for patients was evaluated using YMRS and MADRS.

Video recording is done by a presentation guide including seven tasks such as explaining the reason to come to hospital/participate in the activity, describing happy and sad memories, counting up to thirty, explaining two emotion eliciting pictures. To increase the challenge of automatic discrimination, the Control Subjects were recorded with two additional conditions, where they are asked to portray mania and depression conditions.

To provide a benchmark system and insight about the data, we investigated two different approaches. The first is a direct approach to classify video sessions into BD and normal classes, using audio-visual features. The second is an indirect approach, where we use emotion predictions for Pearson correlation analysis and regression of YMRS drop.

Speech Analysis: Acoustic Feature Extraction

Speech utterances are first separated from the video signal and then a standard set of acoustic descriptors are extracted from the audio signal using the open-source openSMILE tool (Eyben et al, 2013). In our preliminary work, we apply functionals over the whole utterance and compare performances of two sets of functionals. The first set of functionals are those used in INTERSPEECH 2010 baseline features. The second is our proposed set of 10 functionals, which we apply on all LLDs and obtain a supra-segmental feature set of $76 \times 10 = 760$ dimensions.

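### Does the lack of a named paired rank test, and of a stated test for each contrast, undermine the mania versus remission comparison?

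*SAP*

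**What the plan says.** The Protocol, under Neurocognitive Evaluation, times the patients' tests "For patients both in the manic phase(in the first week of hospitalization) and in the remission (at 3rd month after beginning of mania treatment". It then states the two contrasts in a single sentence: "The comparison of bipolar mania neurocognitive functions with both bipolar remission and healthy controls are evalauted". The first is within patients; the second is between groups.

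The SAP, under Neurocognitive Evaluation, first deals with categories ("Categoric variables are compared with Chi-square test") and then says "qualitative variables are compared with dependent and independent sampling t-test and Mann- Whitney U test". The word for the second type of variable is almost certainly a slip for quantitative, since categorical variables already have their test. Spearman appears only for correlation. No signed-rank or sign test is named, no test is tied to a contrast, and no rule says when a rank test replaces a t-test.

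Several outcomes are times, for example "reaction time, delay of stop signal, reaction time for stop signal, total of true stops" in the Stop Signal Test, and for Rapid Visual Processing "Outcome measures cover latency (speed of response), probability of false alarms and sensitivity". Neither document describes their distributions.

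**The concern.** The SAP includes a rank test for non-categorical outcomes, so its authors seem to have expected some non-normal scores. The one they named, Mann-Whitney U, assumes independent samples. For a skewed outcome measured twice in the same patients, the list appears to leave a t-test that may lose power or a rank test that ignores the pairing.

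Mania versus remission is one of only two group comparisons planned for the CANTAB. If the unpaired rank test were used on positively correlated pairs, the p-values would be too large and real within-patient change could be missed. If the t-test were used on very skewed scores, power could also fall. And with nothing written about which test serves which contrast, the choice could be made after seeing the data, over more than a dozen outcome measures.

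**Working it through.** **No figure to reproduce.** The documents state no sample size calculation, effect size, SD or within-patient correlation. From them come the number of patients ("Thirty-five male and sixteen female patients", so 35 + 16 = 51 pairs at most), a two-sided test and the 0.05 level. Assumed: correlation 0.3, 0.5 or 0.7; a shift of 0.4 SD; normal or log-normal scores; all 51 retested unless stated.

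**Step 1: match tests to contrasts.**

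| Contrast | Data | Listed tests that fit |
|---|---|---|
| Mania v remission | same patients twice | dependent t-test |
| Mania v healthy controls | separate groups | independent t-test, Mann-Whitney U |

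Each contrast has at least one valid listed test. The dependent t-test has no natural use in the CANTAB comparisons other than the first row.

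**Step 2: the test that fits, normal scores.** With SD 1, the SE of the mean difference is √(2(1 − ρ)/n). For n = 51 and ρ = 0.5 this is √(1/51) = 0.140, so 0.4/0.140 = 2.857 and power is about Φ(2.857 − 1.96) = Φ(0.897) = 0.815. Simulation (10,000 replicates per setting) gives 80%. At ρ = 0.3 / 0.5 / 0.7 the dependent t-test has 67 / 80 / 95% power and signed-rank 65 / 78 / 94%. Without skew, the listed test is slightly the better one.

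**Step 3: the test that fits, log-normal scores, shift on the log scale, 51 pairs.** Power at ρ = 0.3 / 0.5 / 0.7:

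| Log SD | Dependent t | Signed-rank | Difference (points) |
|---|---|---|---|
| 0.3 | 63 / 77 / 93% | 62 / 77 / 93% | −1 / 0 / 0 |
| 0.5 | 60 / 72 / 90% | 61 / 75 / 92% | 1 / 3 / 2 |
| 1.0 | 44 / 54 / 72% | 57 / 71 / 89% | 13 / 17 / 17 |

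Type I error of the dependent t-test is about 4 to 5% throughout, with the lower values at log SD 1. With 35 pairs the losses are similar: 1 / 2 / 3 points at log SD 0.5 (44 / 57 / 77% against 45 / 59 / 80%) and 10 / 14 / 19 points at log SD 1 (31 / 40 / 57% against 41 / 54 / 76%).

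Log SD 1 is severe. A log-normal variable then has SD/mean = √(e − 1) = 1.31 and skewness (e + 2)√(e − 1) = 4.718 × 1.311 = 6.2.

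**Step 4: move the shift to the raw scale.** The t-test's loss grows to about 4 to 9 points at log SD 0.5 and 13 to 27 at log SD 1. At log SD 0.8 the dependent t-test has 66.9 / 76.6 / 89.7% and signed-rank 88.9 / 95.3 / 99.3%, a loss of 22.0 / 18.7 / 9.6 points. The result therefore depends on the assumed form of the effect as well as on the skew.

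**Step 5: the misuse.** An unpaired test takes the variance of the difference as 2 when it is 2(1 − ρ), so its true level is about 2[1 − Φ(1.96/√(1 − ρ))]. At ρ = 0.3, 1.96/√0.7 = 2.343, which gives 1.9%; at ρ = 0.5, 1.96/√0.5 = 2.772, which gives 0.6%. Simulated Mann-Whitney levels at ρ = 0.3 / 0.5 / 0.7 are 2.0 / 0.7 / 0.1%. With a log-scale shift its power is 49 to 51%. With a raw-scale shift at log SD 1 it is about 99 to 100%, against 96 to 100% for signed-rank. The miscalibration is general; the power penalty is not.

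**The case for a change.** The best argument for a change is the asymmetry. A plan that allows a rank test for independent groups should allow one for pairs, and the remedy costs one sentence and no data. If some outcome were strongly skewed with an additive change, the dependent t-test could give up more than 20 points of power, which is not trivial with 51 patients or fewer. A written assignment would also stop tests being picked after the fact across many outcomes.

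The textual observation stands: the assignment is implied, not written, and no paired rank test is named. The large losses are also real under their assumptions. Two things weaken the argument. First, nothing in the documents supports those assumptions. The timed measures might be skewed, but choosing signed-rank for them would rest on a guess. It would also change what is tested: signed-rank does not test the mean difference, and reading it as a shift in location needs roughly symmetric differences. Second, the freedom to choose lies mainly elsewhere. For the paired contrast the list holds one valid test, so an analyst who follows it has nothing to pick; the open choice between a t-test and a rank test concerns patients versus controls. Adding a second paired test without a selection rule would create a choice where there is none now.

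**Conclusion.** No change follows. This is a gap that competent analysts fill sensibly: the dependent t-test for the patients' two assessments, the independent t-test or Mann-Whitney U against controls. Followed in that way, the plan gives a valid paired analysis whose error rate holds at about 4 to 5% in the settings examined. The cost of having no paired rank test runs from a gain of up to 2 points for the t-test (normal scores) to a loss of up to about 17 points (log-scale shift, log SD 1, 51 pairs) or 27 points (raw-scale shift, log SD 1). Those figures rest on an assumed effect of 0.4 SD, assumed correlations of 0.3 to 0.7 and assumed skew, and the number retested at month 3 is not given. The Mann-Whitney figures describe a misuse that the SAP does not state and that would err towards missed effects, not false positives. Naming signed-rank is a reasonable preference with its own trade-off, not the repair of an error.

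### The voice–CANTAB correlation in mania pools 35 men and 16 women with no adjustment for sex, so sex gaps can create, hide or dilute it

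*SAP*

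**What the plan says.** The last paragraph of the protocol's Neurocognitive Evaluation section states the analysis: "The voice analysis results correlation with neurocognitive functions in bipolar mania is examined". The patient group is given in the opening Study Protocol section: "Thirty-five male and sixteen female patients who were diagnosed as BD type I". The SAP's Neurocognitive Evaluation section supplies the method, "Correlation analysis are done with Pearson and Spearman test", and adds that "all of tests are two-sided", with significance flagged at 0.05 and 0.01.

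Neither document mentions a partial correlation, a sex covariate, analysis by sex, or normalisation of voice features by sex or speaker. Sex enters the design only through matching of the healthy controls, who are not part of this correlation.

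The voice measure is not named. The protocol describes acoustic functionals, "which we apply on all LLDs and obtain a supra-segmental feature set of" 760 dimensions. It also describes an indirect approach, "where we use emotion predictions for Pearson correlation analysis and regression of YMRS drop".

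**The concern.** A correlation over two pooled groups mixes the association within each group with the difference between the group means. When both variables differ by sex, the between-sex part adds to or subtracts from the within-sex part. The pooled coefficient can then be non-zero with no association in men or in women, or near zero when both have one. When only the voice measure differs by sex, the extra spread in voice is unrelated to cognition and pulls the coefficient towards zero.

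The link between voice and cognition is part of the question in the study's title. The pooled coefficient validly describes the mixed sample. Where sex gaps are clear, however, it cannot be read as a link between voice and cognition among patients of the same sex.

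**Working it through.** The documents state no expected correlation or power for this analysis, so there is no planned figure to reproduce.

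**Inputs from the documents.** 35 men and 16 women, n = 51 (Study Protocol section); two-sided 5% tests by Pearson and Spearman (SAP, Neurocognitive Evaluation).

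**Assumed inputs.** Within-sex correlation r (0 or 0.4). Sex gaps D (voice) and d (CANTAB) in within-sex SDs, shown as a range. Normal data, complete for all 51 patients, with equal spread in the two sexes unless stated.

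**Formula.** With pq = (35/51)(16/51) = 560/2601 = 0.2153,

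pooled r = (r + pq·D·d) / √[(1 + pq·D²)(1 + pq·d²)].

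- Create (r = 0, D = 1, d = 0.5): 0.1077 / √(1.2153 × 1.0538) = 0.1077 / 1.1317 = 0.095.
- Dilute (r = 0.4, D = 2, d = 0): 0.4 / √1.8612 = 0.293.
- Hide (r = 0.4, D = 1, d = -0.5): (0.4 - 0.1077) / 1.1317 = 0.258.

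The critical |r| is 0.2759 pooled (49 df) and 0.2787 with sex partialled out (48 df).

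**Rejection rates by simulation, 40,000 replicates per row.**

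No within-sex association (r = 0):

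| Gaps D/d | Pooled r | Pearson pooled | Pearson partial | Rank pooled | Rank partial |
|---|---|---|---|---|---|
| 0.3/0.3 | 0.019 | 5.1% | 4.9% | 5.0% | 4.9% |
| 0.5/0.5 | 0.051 | 6.5% | 5.0% | 6.5% | 5.1% |
| 1/0.3 | 0.058 | 6.8% | 5.0% | 6.7% | 5.0% |
| 1/0.5 | 0.095 | 10.2% | 5.0% | 10.0% | 5.1% |
| 2/0.5 | 0.154 | 19.2% | 4.9% | 18.3% | 5.0% |
| 2/0 | 0 | 4.9% | 5.0% | 5.0% | 4.9% |

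Within-sex r = 0.4, Pearson:

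| Gaps D/d | Pooled r | Power pooled | Power partial |
|---|---|---|---|
| 0/0 | 0.400 | 84.3% | 83.6% |
| 0.3/0 | 0.396 | 83.3% | 83.5% |
| 0.5/0 | 0.390 | 82.1% | 83.6% |
| 1/0 | 0.363 | 75.5% | 83.6% |
| 2/0 | 0.293 | 55.4% | 83.5% |
| 0.3/-0.3 | 0.373 | 78.1% | 83.5% |
| 0.5/-0.3 | 0.355 | 73.7% | 83.7% |
| 1/-0.5 | 0.258 | 44.3% | 83.2% |
| 0.5/0.5 | 0.431 | 89.7% | 83.6% |

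Spearman does not escape the problem. Rank power, pooled against partialled, is 79.8% vs 79.0% at 0/0, 50.0% vs 77.5% at 2/0, and 39.5% vs 78.0% at 1/-0.5.

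**Unequal spread (r = 0).** If women's SD is 1.5 times men's on both measures and there are no mean gaps, Pearson rejects 6.8% pooled and 6.9% partialled, and the rank test 5.6% either way. Adding gaps of 1/0.5 gives 9.9% vs 7.0% (Pearson) and 7.5% vs 5.4% (rank).

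**The case against.** The strongest objection is that the harm rests on numbers the documents do not contain. No sex gap is given for any voice measure or CANTAB outcome, and a false correlation needs a gap in both. At modest gaps the effect is slight: 5.1% at 0.3/0.3, 6.5% at 0.5/0.5. This stands, and it is why the result is given as a range.

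Second, the affect scores are arguably the likelier voice measure. The protocol assigns emotion predictions to Pearson correlation, and the SAP sends the feature vectors to PLS and Extreme Learning Machines. For affect scores the sex gap may be small. This also stands, but the sentence on voice and neurocognition does not name its measure, so the acoustic features are not excluded.

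Third, adjustment is partly a choice of what to estimate, and age, education, treatment or severity could be argued for as well. The pooled coefficient is indeed valid for the mixed sample. Reporting both coefficients meets this point, and nothing here rules out other covariates.

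Fourth, the absence of adjustment is inferred from a very short SAP, and feature processing is partly left to cited work. That is fair as to practice. The plan as written, however, names only unadjusted tests.

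Fifth, the remedy is partial. It removes mean gaps but not unequal spread, and it assumes a common within-sex slope that 16 women can hardly test. With unequal spread it performs about the same as the pooled test or better in the cases examined.

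Last, the protocol lists about 18 CANTAB outcomes (4 + 6 + 5 + 3) with no multiplicity rule, beside which a rise to 6–7% per test is minor. That is a separate matter and does not help with dilution or hiding.

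**Conclusion.** The concern holds in its conditional form. The mechanism follows from the algebra at a 35/16 split; its size in these data is unknown. With gaps of about 0.3 SD or less in both measures, the pooled and adjusted analyses nearly agree on false positives, though opposite gaps of that size already cost about 5 points of power (78.1% vs 83.5%). With a 1 SD voice gap and a 0.5 SD CANTAB gap, false positives double to about 10%. If those gaps oppose a within-sex correlation of 0.4, power falls to 44% from about 83%. The largest false-positive rate tabulated (19%) and the dilution to 55% power apply only to a voice measure with a 2 SD sex difference.

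These figures assume normal, complete data and, except where stated, equal spread in the two sexes. The change is worth making because it is nearly free; confidence that it matters here is moderate, since that depends on which voice measure is used.

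**What to change.** Add one sentence to the SAP's Neurocognitive Evaluation section: the voice–CANTAB correlation in mania will be reported as a partial correlation given sex (Pearson on the values, or on ranks where Spearman would be used), with the unadjusted correlation alongside. The same step may be applied to the YMRS–CANTAB correlation for consistency; no bias is claimed there.

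This is a standard SPSS procedure using a variable already recorded. It costs one degree of freedom, and the critical |r| rises from 0.276 to 0.279. If sex has no effect, power at r = 0.4 falls by 0.7 points for Pearson (84.3% to 83.6%) and 0.8 points for ranks (79.8% to 79.0%). If both gaps run in the same direction as the association, the adjusted test rejects less often (90% to 84% at 0.5/0.5), because part of the pooled correlation was the sex difference itself.

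### At least 72 cognitive tests are each judged at two-sided p<0.05 with no stated multiplicity adjustment, primary measure or exploratory label, so about four or more chance stars are expected if no effects exist

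*SAP*

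**What the plan says.** The Protocol's Neurocognitive Evaluation section sets out four CANTAB tests and their outcomes:

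- "Cambridge Gambling Test: Deliberation time, quality of decision making , risk taking, aversion delay" (4 outcomes)
- "Emotion Recognition Test: Total rate of happiness, sadness, anger,disgust, fear, surprise" (6)
- "Stop Signal Test: Rate of succesful stops, reaction time, delay of stop signal, reaction time for stop signal, total of true stops" (5)
- "Rapid Visual Processing: Outcome measures cover latency (speed of response), probability of false alarms and sensitivity" (3)

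The closing paragraph of that section gives these outcomes four uses. For patients in mania, "first YMRS ratings are correlated with first week neurocognitive functions of the same group". The manic-phase scores are compared with the same patients' scores in remission and with those of healthy controls. Finally, "The voice analysis results correlation with neurocognitive functions in bipolar mania is examined".

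The SAP's Neurocognitive Evaluation section names the software, the chi-square, t, Mann-Whitney, Pearson and Spearman tests, and the rule "Statistical significance is *= $p<0.05$, = $p<0.01$, all of tests are two-sided". It says nothing about multiplicity. Neither document states a primary cognitive outcome, a lead comparison, a testing order or an exploratory status for these analyses, or how many voice results are correlated with cognition.

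**The concern.** The significance rule applies to each test separately, and nothing else in either document governs which results count as findings. With many outcomes put to several uses each, some will pass 0.05 when nothing is there. A reader shown a table of stars could not separate cognitive correlates that would replicate from those that would not.

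The correlations have a second problem. With 51 patients, a correlation needs an absolute value of about 0.28 to earn a star, so a weaker true correlation that happens to be starred will be overstated. The choice between Pearson and Spearman, and between the t-test and Mann-Whitney, is also left open, which adds room for selection on top of the number of outcomes.

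**Working it through.** The documents give no count of tests, familywise error rate or power calculation, so there is no figure of theirs to reproduce.

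**Inputs.** From the Protocol's Neurocognitive Evaluation section: 4 + 6 + 5 + 3 = 18 outcomes, with three non-voice uses and one voice use. From the SAP: two-sided thresholds of 0.05 and 0.01. From the Protocol's opening section: 35 + 16 = 51 patients and 24 + 16 = 40 controls. The number of voice results, V, is not stated. V = 1 is the minimum if any voice correlation is run. V = 3 assumes one output from each of the three affect classifiers. V = 6 assumes four emotion-class scores plus valence and arousal.

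**Number of tests.** k = 18 × (3 + V) = 54 + 18V.

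**Expected chance stars if every null is true.** 0.05 × k. Dependence between the tests does not change this.

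**Chance of at least one, if the tests were independent.** 1 − 0.95^k.

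| Voice results V | Tests k | Expected at p<0.05 | Expected at p<0.01 | Chance of at least one at p<0.05 |
|---|---|---|---|---|
| 0 (non-voice only) | 54 | 2.7 | 0.54 | 0.937 |
| 1 | 72 | 3.6 | 0.72 | 0.975 |
| 3 (assumed) | 108 | 5.4 | 1.08 | 0.996 |
| 6 (assumed) | 162 | 8.1 | 1.62 | 0.9998 |

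**Power cost of adjusting, taken at the Bonferroni bound.** All figures are at 80% power and assume complete CANTAB data. Benjamini-Hochberg is never stricter than Bonferroni within the same family, so these are upper limits on the loss.

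- Mania vs controls, 51 vs 40, two-sample t-test: the detectable standardised difference d is 0.60 at alpha 0.05 and 0.83 at 0.05/18 = 0.0028.
- Correlations at n = 51, Fisher z: r = tanh[(z for 1 − alpha/2 + 0.842)/√48].
  - At 0.05: tanh(2.802/6.928) = 0.38.
  - At 0.05/18: tanh(3.833/6.928) = 0.50.
  - At 0.05/108 (six voice scores × 18 outcomes): tanh(4.343/6.928) = 0.56.

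**The case against.** **The size depends on a voice count that the plan does not give.** This stands. A reader might take 162 as the minimum, but it arises only with six voice scores. The SAP's Regression Model section names valence, arousal and affect scores as predictors of YMRS change, not as the set to be correlated with cognition. The firm figures are 54 tests, and 72 once any voice result is used.

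**A reader might infer that all 760 acoustic features will be tested against cognition.** The documents do not support that. The Protocol gives that dimension for a "supra-segmental feature set" in its account of acoustic feature extraction and says nothing there about testing features one by one. Its description of the indirect approach bases the Pearson correlations on emotion predictions. That reading still needs to be written down, because the sentence on voice and cognition does not define its variables.

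**Silence is not refusal.** This also stands. The SAP does not say that results will be left unadjusted; it states no adjustment. But the paragraph is otherwise complete on tests, threshold and sidedness, and an analyst who followed it would star on the raw p-value.

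**The error figures are conditional.** The expected counts hold when every null is true, and shrink with the number of true nulls, which is unknown. Manic patients may well differ from controls on several measures. The 94% and 97.5% assume independence. Some outcomes overlap, such as the two measures of successful stopping, and the same manic-phase scores enter all four uses, so with positive correlation the chance of at least one is lower.

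**The work may be exploratory.** The Protocol states no confirmatory hypothesis for cognition, and an explicit exploratory label with complete reporting would be a defensible alternative. Neither document applies that label, and a two-level star rule invites confirmatory reading.

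**Conclusion.** The concern holds in this form: at least 72 cognitive tests face a per-test two-sided 0.05 rule, with nothing stated to limit or rank the claims that follow. If no effects exist, 3.6 chance stars are expected at 72 tests and 8.1 at 162, the latter only under the six-score assumption. The 54 non-voice tests alone give 2.7, and about a 94% chance of at least one if the tests were independent.

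This is more than missing detail, because the rule as written is enough to produce unreliable findings. It bears on interpretation and not on the data collected. The documents do not show that any particular result will be false, or that the investigators have decided against adjustment. The change should be made because it is cheap and needs no new data.

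**What to change.** In the SAP's Neurocognitive Evaluation section:

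1. Define four families: YMRS-cognition, mania-remission, mania-control and voice-cognition. The first three have 18 tests each; the fourth has 18 for each voice score.
2. Apply Benjamini-Hochberg at 5% within each family. Base the word significant and the stars on the adjusted value.
3. Report all results, with unadjusted p-values and confidence intervals, whether or not they are starred.
4. State that the voice family consists of the affect-classifier scores, list them, and exclude the 760 raw acoustic features.
5. Name one prespecified test for each comparison, so that Pearson and Spearman, or the t-test and Mann-Whitney, are not both available for the same data.

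The cost is a revised paragraph, a few lines of analysis, fewer starred results and some power. The loss is at most that of Bonferroni within the family. Over 18 tests, the detectable d for 51 vs 40 rises from about 0.60 to 0.83, and the detectable r at n = 51 from about 0.38 to 0.50 (about 0.56 over 108 voice tests). Control within families does not control error across all four, and the SAP should say so. The Protocol reports participants as already included, so the amendment should also state whether the cognitive data had been analysed when it was made.
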